The need to understand the impact of smoked THC and CBD in clinical populations is supported by 3 prior studies by Valerie Curran’s group at University College London. In a 2008 study, hair samples collected from a population of 140 users of a variety of illicit substances were screened for THC and CBD. Subjects who screened positive for THC alone showed higher levels of positive schizophrenia-like symptoms compared to both those who screened negative for cannabinoids and those who screened positive for THC and CBD, suggesting that smoked CBD may have antipsychotic properties. A second study in 2010 in which subjects were assessed after using their chosen strain of cannabis indicated that smokers of high CBD:THC strains showed a decreased attentional bias towards drug and food stimuli and less self-reported liking of cannabis stimuli. These data suggest that CBD may mitigate the effects of THC and may have utility as a treatment for cannabis dependence. Finally, in a 2014 study of 48 cannabis-using subjects who received inhaled THC, CBD, THC+CBD, and placebo, subjects showed improved recognition of facial affect without any effect on feelings of being “stoned” after receiving CBD alone. In contrast, THC produced a reduction in facial affect recognition, while THC+CBD and placebo showed no effect. Both THC alone and THC+CBD in combination increased feelings of being “stoned” relative to placebo. The results of this laboratory study provide early evidence that agents that target the endocannabinoid system may produce contrasting neurocognitive effects. In total, the findings from these studies suggest that further study of the impact of THC and CBD in psychiatrically ill populations (including OCD) is warranted.

Specific Aims and Hypotheses

Specific Aims and Hypotheses

Specific Aims:

To compare the effects of High THC (5-10%)/Low CBD (<1%) marijuana, Low THC (<1%)/High CBD (>10%) marijuana, and placebo (0% THC and CBD) marijuana in adults with primary OCD who also occasionally smoke marijuana.

Specific Hypothesis:

In the acute setting, smoked marijuana in both high THC/low CBD and low THC/high CBD concentrations will lead to a reduction in symptoms in adults with primary OCD who are also occasional marijuana smokers as compared to placebo.

Description of Subject Population

Sample #1

Specify subject population

Adults who meet DSM 5 criteria for OCD who are also occasional marijuana smokers

Number of completers required to accomplish study aims

15

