Laboratory Sessions: Participants will be instructed that they should not smoke either marijuana or cigarettes on the morning of a session (beginning at midnight). We will do a carbon monoxide (CO) test upon their arrival in the laboratory to verify nothing was recently smoked. Participants will also be given a breathalyzer test to ensure that they did not drink alcohol prior to arrival. At each visit, urine samples will be tested for drug use, and, for women of child-bearing age, for pregnancy. Subjects who are found to be pregnant will be discontinued from the study, but will receive payment for those procedures that they have already completed. Participants with high COs or those testing positive for drugs other than marijuana will be re-scheduled and possibly excluded from further participation. Patients will then receive either high THC (5-10%)/low CBD (<1%) marijuana, low THC (<1%)/high CBD (>10%) marijuana, or placebo (0% THC and CBD). The marijuana used in the study will be provided by the NIDA. We will guide participants through smoking individual puffs of marijuana using cue-dosing procedures until 50% of the cigarette has been smoked. Specifically, for each puff, participants will be instructed to inhale for 5 seconds and hold each puff in the lungs for 10 seconds. There will be approximately a 40-second interval between each puff. For the first hour after marijuana administration, clinical ratings, scales, and BP/HR will be obtained every 20 minutes. During the second hour, these measures will be repeated once every half-hour, and then again at the conclusion of the third hour (see Table 1). The session will end after the third hour. Participants will be allowed to leave the facility when they pass the field sobriety test, and will be instructed not to drive a car or use other drugs or alcohol for at least 8 hours after marijuana administration.

Table 1. Session Schedule

| TIME (min) | EVENT |
|------------|--|
| -50 | CO, collect urine, breathalyzer, start breakfast |
| -30 | Finish breakfast (set timer for 30 min), balance, TLFB, BP/HR, VAS, YBOCCS, STAI |
| 0 | Marijuana administration |
| 20 | BP/HR, VAS, YBOCCS, MRF, STAI |
| 40 | BP/HR, VAS, YBOCCS, MRF, STAI |
| 60 | BP/HR, VAS, YBOCCS, MRF, STAI |
| 90 | BP/HR, VAS, YBOCCS, MRF, STAI |
| 120 | BP/HR, VAS, YBOCCS, MRF, STAI |
| 180 | BP/HR, VAS, YBOCCS, MRF, STAI, Field Sobriety Test, participant discharge |

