** BP/HR = blood pressure and heart rate; VAS = Visual Analogue Scale; YBOCCS = Yale-Brown Obsessive-Compulsive Challenge Scale; MRF = Marijuana Rating Form; STAI = State/Trait Anxiety Inventory; TLFB = Marijuana Timeline Followback

Patients will be required to take public transportation to and from the laboratory each session, for which they will be reimbursed. Study clinicians will conduct the Field Sobriety Test. After confirming that the participant has passed the Field Sobriety Test, the patient will be allowed to leave the laboratory. If a participant is still impaired at the end of the session, she or he will be asked to remain in the laboratory until the effects wear off, and will be paid extra (i.e. \$10 per hour for any additional time in the laboratory). In the event that the impairment does not resolve in a timely manner, a study physician will determine whether the person can leave the laboratory or if further action is needed. It is worth noting that in our experience, it is exceedingly rare (<1% of all participants) for marijuana smokers to remain intoxicated several hours after smoking marijuana in the laboratory.

Laboratory Facility: Experimental sessions will be conducted in the Substance Use Research Center (SURC) located on the 3rd floor of the NYS Psychiatric Institute.

Safety Measures: Vital signs (heart rate and blood pressure) will be monitored in each session. If SBP > 180 mmHg, DP > 110 mmHg, or HR > 120 bpm, these measures will be taken 2 additional times at 2 min intervals: A physician will see the participant immediately if blood pressure or heart rate remain above these levels for 3 continuous readings.

Data Analysis: A between and within-subject repeated measures analysis of variance (ANOVA) with planned comparisons will be implemented to determine the effects of marijuana on OCD symptoms

You can upload charts or diagrams if any

Criteria for Early Discontinuation

Criteria for Early Discontinuation

Participants are free to withdraw from the study at any time for any reason. Study doctors are to discontinue patients from the study if patients:

- Request an early discontinuation or withdraw consent.
- Experience a serious or intolerable adverse event that prevents the patient from continuing.

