Cannabis Effects: We will use a random-effects linear mixed model to evaluate changes in each continuous outcome (YBOCCS, OCD-VAS, STAI-S MRF, cardiovascular measures) as a function of condition (THC, CBD, placebo), time point, and their interaction. Mixed-effects modeling accounts for clustering of repeated measures within subjects, allows time to be modeled as a continuous rather than categorically, and has been used in similar acute pharmacological challenge studies (Rodriguez et al. 2013). The model will include participants as a random effect, condition and time as fixed within-subjects factors, the interaction between condition and time, and a random intercept. Given that the interval between sessions increases over the course of each session, we will model time as a continuous variable. We will use contrasts within each mixed-effects linear regression model to estimate differences in outcomes between both active cannabis varieties and placebo at different time points. All statistical tests will be conducted using an alpha level of 0.05, two-tailed.

Other Effects: Though we have no a priori hypotheses about the effects of age, gender, comorbid diagnoses (e.g. MDD), or other factors that might influence our participants' response to cannabis, we will nonetheless explore the possibility of such effects by including these factors as covariates in separate analyses.

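### No primary OCD scale, time or success rule is set: if either variety at any of six times counts, the false-reduction rate is about 11% on YBOCCS and 17–21% across both OCD scales (15 completers, independent residuals, between-scale correlation 0.8 to 0)

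*Combined protocol and SAP*

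**What the plan says.** The Cannabis Effects part of the Data Analytic Plan fits a mixed model to "evaluate changes in each continuous outcome (YBOCCS, OCD-VAS, STAI-S MRF, cardiovascular measures"). Two of these, YBOCCS and OCD-VAS, measure OCD symptoms, and neither is named primary. "The model will include participants as a random effect, condition and time as fixed within-subjects factors", with their interaction and a random intercept. Time is continuous. Contrasts within each model are to "estimate differences in outcomes between both active cannabis varieties and placebo at different time points". The times are not listed. The error rule is one sentence: "All statistical tests will be conducted using an alpha level of 0.05, two-tailed".

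The other places where a decision rule might stand do not supply one:

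- **Study Procedures, Laboratory Sessions:** "For the first hour after marijuana administration, clinical ratings, scales, and BP/HR will be obtained every 20 minutes". With the later ratings in Table 1, this gives post-dose ratings at 20, 40, 60, 90, 120 and 180 min, none singled out.
- **Study Procedures, Data Analysis:** a repeated-measures ANOVA is mentioned in which "planned comparisons will be implemented to determine the effects of marijuana on OCD symptoms". The comparisons are not listed.
- **Specific Aims and Hypotheses:** "smoked marijuana in both high THC/low CBD and low THC/high CBD concentrations will lead to a reduction in symptoms in adults". No scale, time or decision rule follows.
- **Background, Significance and Rationale:** response is equated with a significant symptom reduction, without a scale, time or threshold.
- **Description of Subject Population:** the entry "Number of completers required to accomplish study aims" is 15, with no derivation.

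**The concern.** Two varieties, two OCD scales and up to six times give as many as 24 OCD contrasts, each tested at 0.05 two-sided. If any one of them can be reported as support for the hypothesis, the chance of a false claim of symptom reduction is well above that of a single test. If both varieties must succeed, the chance is low when neither works, but the second variety remains exposed when the first truly works. Nothing in these documents prevents the scale, the time and the success rule from being chosen after the results are known. The plan uses the language of exploration only for covariates such as age and gender. The OCD contrasts carry a directional hypothesis.

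**Working it through.** **Figure to reproduce.** The documents give no power, effect size or familywise error rate. The only stated figure is the per-test level: 0.05 two-tailed, so 0.025 in the direction of reduction. One null contrast at 60 min in the planned model, with independent residuals, rejects in that direction 2.6% of the time, which agrees.

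**Inputs from the documents.** n = 15 completers; 3 sessions each; 7 ratings per session (−30, 20, 40, 60, 90, 120, 180 min); condition × linear time; participant intercept only; contrasts of two varieties with placebo.

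**Assumed.** Complete data; no effect of either variety unless stated; independent residuals unless stated; between-scale correlation 0 to 0.8; contrasts tested at all six post-dose times unless stated.

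**Test statistic.** The mean rating time is 480/7 = 68.6 min and the sum of squared deviations is Sxx = 28,486. Write m and s for a condition's fitted mean and slope. For variety a against placebo P at time τ,

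t = [(m_a − m_P) + (s_a − s_P)(τ − 68.6)] / {σ̂ √[(2/15)(1/7 + (τ − 68.6)²/28,486)]}

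with 15×3×7 − (15 + 5) = 295 degrees of freedom. The participant intercept cancels because everyone has all three sessions.

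**How far the six contrasts overlap.** With g(τ₁,τ₂) = 1/7 + (τ₁ − 68.6)(τ₂ − 68.6)/28,486, the correlation between two times is g(τ₁,τ₂)/√[g(τ₁,τ₁)·g(τ₂,τ₂)].

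- 60 and 90 min: 0.136/√(0.145 × 0.159) = 0.90.
- 20 and 180 min: −0.047/√(0.226 × 0.579) = −0.13.

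Neighbouring times are nearly the same test, but the first and last are almost separate tests. The answer therefore lies well below the 1 − 0.975¹² = 26.2% of twelve independent tests, and well above 2.5%.

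**Simulated false-reduction rates, either variety** (60,000 null runs per setting where three correlations are shown, otherwise 40,000):

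| Analysis | YBOCCS | Either OCD scale (correlation 0 / 0.5 / 0.8) |
|---|---|---|
| Planned model, six times | 11.2–11.3% | 21.0 / 19.3 / 16.6% |
| Planned model, 20 and 180 min only | 9.0–9.2% | 17.2 / – / 13.6% |
| Planned model, 60 min only | 4.5–4.7% | 8.8 / – / 7.1% |
| Planned model, six times, unmodelled session effect 10% | 17.3–17.6% | 31.7 / 28.1 / 24.7% |
| Same, session effect 20% | 22.5–22.7% | 40.0 / 35.4 / 31.1% |
| Session random effect fitted, effect 10% | 10.1–10.2% | 19.2 / – / 15.2% |
| Same, effect 20% | 9.2–9.5% | 17.8 / – / 13.8% |
| Separate paired t tests, six times | 24.5% | 43.3 / – / 36.2% |

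The session effect is an assumed share of within-subject variance. The paired-test row is one assumed reading of the unlisted ANOVA comparisons.

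**If both varieties must succeed on YBOCCS** (planned model, six times, independent residuals): 1.5–1.6% when neither works. When the first variety truly works, the false rate for the second is that of one variety over six times, 6.2–6.4%.

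**Cross-checks.** A separate calculation with 200,000 replicates gave 11.2% on YBOCCS and, across both scales, 21.1% at correlation 0, 17.6% at 0.7 and 15.1% at 0.9. Fitting the mixed model itself to 600 simulated trials gave 10.2% on YBOCCS (simulation standard error about 1.2 points). Changing n to 12 or 20 leaves the YBOCCS rate at 11.2–11.4%.

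**The case against.** The hypothesis names both varieties. Read as a requirement that both succeed, it gives about 1.5%, below the 2.5% of a single test. The plan does not say that all six times will be tested, and with one time the YBOCCS rate is 4–5%. An analyst might also test the interaction first, or condition and interaction jointly, before looking at contrasts; with independent residuals that holds the YBOCCS rate to about 2.3% or 2.7%. YBOCCS is the dedicated OCD scale and is listed first, while the VAS also covers mood, anxiety and drug effects. The two scales rate the same symptoms, so zero correlation is the less plausible end of the range. The trial is registered, and its record, not available here, may name a primary outcome. Finally, this is a small laboratory study that could properly be called exploratory.

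These points show how much the error rate depends on the rule, but the documents adopt none of the rules that would keep it low. They state no gate, do not turn the word both into a decision rule, do not limit the times and do not rank the scales. What stands is that the high figures are conditional on an either-variety claim, that the session-effect and paired-test figures rest on assumptions the documents cannot settle, and that the conclusion is confined to these documents.

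**Conclusion.** The concern holds. On YBOCCS, the false-reduction rate when neither variety works runs from about 1.5% (both varieties required) to about 11% (either variety, any of six times). Across both OCD scales the either-variety rate is 17–21%, for between-scale correlation 0.8 to 0. These figures assume the planned linear-time model, 15 completers with complete data and independent residuals. They are not a ceiling: an unmodelled session effect of an assumed 10–20% of within-subject variance raises the either-variety, six-time rates to about 17–23% and 25–40%. Fitting that effect brings them back only to about 9–10% and 14–19%, so the missing decision rule matters in its own right. The plan should be amended before unblinded analysis.

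**What to change.** Before unblinded analysis:

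1. Name one primary OCD scale, for example YBOCCS, and one post-dose contrast with placebo per variety. One option is each participant's mean of the six post-dose ratings in a session, compared between sessions.
2. State the success rule: Holm at 0.05 across the two contrasts if either variety can support a claim, or each contrast at 0.05 if both are required.
3. Label the other OCD scale, individual times, STAI-S, MRF and cardiovascular measures secondary or exploratory, and report them with intervals.
4. If a mixed model is kept for the primary contrast, add a participant-by-session random effect.
5. If the study is meant only to explore, say so, report all contrasts as estimates with intervals, and make no symptom-reduction claim from p-values.

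**Check of the option.** The six-rating mean with paired t tests and Holm gave any rejection 4.6–4.9% and false reduction 2.3–2.4% at session effects of 0, 10 and 20%. False reduction for the second variety when the first works was about 2.5%. A single contrast at 85 min (the mean post-dose time) from the participant-intercept-only model is not a safe substitute: with Holm, any rejection was 4.5–4.8%, 13.5–13.7% and 23.1–23.4% at the same session effects.

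**Cost.** SAP wording and a small change to the primary analysis. In a paired approximation with 15 completers (differences in units of the SD of participant differences), power at 0.78 falls from 80% to no lower than 69% under Holm, and the difference detectable with 80% power rises from 0.78 to at most 0.88. If both varieties are required, power to win both at 0.78 each is about 68% (correlation 0.5 between the two differences, assumed). A raw six-time mean halves an effect present at only three times. The 85-min model contrast keeps 91% of a constant post-dose effect, 38% of one confined to 20–60 min and 53% of one confined to 90–180 min. The choice of contrast should reflect the time course expected.

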Background, Significance and Rationale

Background, Significance and Rationale

Previous research has suggested that the endocannabinoid system may serve a regulatory function in frontal-striatal brain circuits which have been implicated in anxiety disorders and Obsessive Compulsive Disorder (OCD) (Lutz et al. 2015, Gremel et al. 2016). In addition, there is an emerging body of evidence which demonstrates a potential role for drugs that target cannabinoid receptors in the treatment of anxiety disorders and Tourette's syndrome (Curtis et al. 2009, Müller-Vahl et al. 2013, Blessing et al. 2015). Data from animal studies (Deiana et al. 2011, Nardo et al. 2013, Breuer et al. 2016) suggest a potential benefit to these compounds in OCD as well. However, to date studies in humans are limited to case reports (Schindler et al. 2008). The purpose of this double-blind, placebo-controlled, within-subject study is to examine the effects of different cannabinoids, delivered in a laboratory setting, on adults with primary OCD. In order to accomplish this, adults with OCD who are also occasional marijuana smokers will be recruited for 3 outpatient laboratory sessions over the course of 2-3 weeks. In the laboratory, patients will receive different combinations of the cannabinoids tetrahydrocannabinol (THC, the active ingredient in the marijuana plant) and cannabidiol (CBD, a cannabinoid constituent of marijuana which has demonstrated therapeutic potential across a variety of psychiatric disorders including depression, anxiety, and psychosis [Campos et al. 2012]) or placebo. We will then measure whether or not patients respond to these agents (i.e. experience a significant reduction in their OCD symptoms) in the acute setting.

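### Adding age, gender and comorbidity as covariates tests symptom level, not response to cannabis; the factor-by-condition terms need to be named

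*Combined protocol and SAP*

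**What the plan says.** The Other Effects paragraph of the Data Analytic Plan disclaims prior hypotheses but wants to look at age, gender, comorbid diagnoses and "other factors that might influence our participants' response to cannabis". The only method it gives is: "we will nonetheless explore the possibility of such effects by including these factors as covariates in separate analyses".

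The model these analyses build on is in the Cannabis Effects paragraph: "The model will include participants as a random effect, condition and time as fixed within-subjects factors", plus the condition-by-time interaction and a random intercept. Its results are contrasts, described as "differences in outcomes between both active cannabis varieties and placebo at different time points". Condition by time is the only interaction the plan names.

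The shorter Data Analysis statement under Study Procedures has "A between and within-subject repeated measures analysis of variance (ANOVA) with planned comparisons", but names no between-subject factor and no interaction.

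Two other places fix the meaning of response. The Specific Hypothesis is about symptom reduction in adults with OCD "who are also occasional marijuana smokers as compared to placebo". The Background section describes a placebo-controlled, within-subject study, so each participant is meant to receive all three conditions.

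**The concern.** A factor that influences response to cannabis must change the difference between active cannabis and placebo. That is an interaction between factor and condition. A covariate in its usual sense is an additive term, and here each named factor is constant across a participant's three sessions. Such a term shifts all of a participant's scores by the same amount and cancels from every within-participant comparison.

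Its coefficient can be large when the factor has nothing to do with response, for example if one gender simply has higher symptom scores throughout. It can be near zero when the factor does alter response. Either result could be reported as evidence about who responds. The main cannabis-placebo comparison is not affected by this choice. Factors that vary from session to session are also outside the point.

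**Working it through.** The documents give no power calculation, effect size or SD, so there is no stated figure to reproduce. The check is algebra, then simulation under stated assumptions.

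**Inputs from the document.** Three conditions per participant; six post-dose times (20, 40, 60, 90, 120, 180 min; Table 1); 15 completers from 20 enrolled; gender about 1:1, hence 7 v 8; two-sided 0.05.

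**Assumptions.** Within-person variance 1, of which a share *s* is common to a session; between-participant variance 1; *s* = 0.4 unless varied.

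**Step 1: the additive term cancels.** Give participant *i* the term a·g_i in all conditions. The participant's active-minus-placebo difference contains a·g_i − a·g_i = 0. In fitted models with complete data, adding the covariate changed the condition contrasts and time slopes by less than 1e-14. With 20 enrolled and 5 or 8 stopping after session 1 or 2, the THC-placebo contrast moved by a median of 0.001 to 0.004 (maximum 0.043), against an SE of 0.13 to 0.15.

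**Step 2: what the coefficient estimates.** Let L be the group difference in level, and M_T and M_C the group differences in THC and CBD response. On post-dose scores the additive coefficient has expectation L + (M_T + M_C + 0)/3, the zero being placebo. Mean results from 4,000 datasets per scenario:

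| Scenario | Formula | Covariate | Factor-by-THC |
|---|---|---|---|
| A: L = 1, no response difference | 1 | 1.01 | 0.00 |
| B: M_T = −1 | −1/3 | −0.33 (SE 0.55) | −1.01 (SE 0.52) |
| C: M_T = −1, M_C = +1 | 0 | 0.01 | −1.03 |

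If both varieties are modified by +1, the formula gives 2/3 = 0.67. With the pre-dose time included it gives 2/3 × 6/7 = 0.57, which matches a separate simulation.

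**Step 3: change scores.** The plan does not say whether raw or change scores are modelled. With change from baseline, the coefficient is average change over all three conditions. A factor linked to equal change under placebo and both active varieties (true interaction zero) gave a coefficient of 1.01, significant in 91% of 150 datasets.

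**Step 4: precision of the interaction.** Times have mean 85 and sum of squares 17150. At time *t*:

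Var = 2(1/7 + 1/8)·[s + (1−s)/6 + (1−s)(t−85)²/17150].

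At t = 85 and s = 0.4: 0.5357 × 0.5 = 0.268, so SE = 0.518.

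**Step 5: the random effects matter.** The plan's model has a participant intercept only, which pools the session stratum (26 df, mean square 6s + 1 − s) with the within-session stratum (219 df, 1 − s). At s = 0.4 the pooled variance is (26 × 3.0 + 219 × 0.6)/245 = 0.855, and the reported SE is √(0.5357 × 0.855/6) = 0.276.

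| Session share | 0% | 20% | 40% | 60% | 80% |
|---|---|---|---|---|---|
| True SE | 0.30 | 0.42 | 0.52 | 0.60 | 0.67 |
| Reported SE, participant intercept only | 0.30 | 0.29 | 0.28 | 0.26 | 0.25 |
| 95% CI coverage | 95% | 82% | 70% | 61% | 54% |

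A participant-by-session random effect restores coverage to 94% (normal quantile) or 95% (Satterthwaite df) throughout. A REML check at s = 0.4 (200 datasets) gave 75% without it and 98% with it. The latter is about two simulation standard errors above 95% (0.03/0.0154 = 1.9).

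**Step 6: what the corrected analysis can detect.** With 26 df, t = 2.06. The 95% half-width runs from 0.61 SD (s = 0) to 1.37 SD (s = 0.8). 80% power needs a subgroup difference of 0.87 to 1.94 SD, or 1.51 SD at s = 0.4.

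**The case against.** The strongest objection is that the wording is loose rather than wrong. The plan does not exclude interactions, and the authors may have meant them. That is possible, but the ordinary meaning of covariate is additive, and an analyst following the text would not know to add the interaction. If interactions were intended, the edit only states the intention.

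Second, the additive term is not wholly blind to response. If a factor modifies both varieties in the same direction by 1 SD, which is plausible given that the hypothesis expects both to reduce symptoms, the coefficient averages about 0.67. This stands. Scenario C is the extreme case. But 0.67 is a diluted figure that cannot be told apart from a level difference of 0.67.

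Third, the analysis is exploratory and 15 completers give little precision even when it is done correctly. This also stands and limits the importance. It argues for intervals and an exploratory label, not for estimating a different quantity.

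Fourth, the session random effect is a separate modelling question that would bear equally on the main contrasts. That is fair: Step 5 does not show harm from the quoted sentence. It is included because adding the interaction to the plan's random-intercept model could give intervals that are much too narrow.

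Fifth, there would be many intervals: three factors, five outcome groups, two contrasts and up to six times give 180. Comorbidity may also be sparse, since exclusion criterion 4 covers major depressive disorder requiring medical intervention. At s = 0.4 a 2 v 13 split has a half-width of about 1.56 SD, against 1.06 for 7 v 8. Both are good reasons for restraint in reporting.

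**Conclusion.** The concern holds. For factors constant within a participant, the stated method does not address the stated question. That conclusion follows from the design: it is exact with complete data, very nearly so with the dropout examined, and needs no variance assumption. The sizes in the scenarios, the SEs and the coverage do rest on assumed variances and a 7 v 8 split. The session share is unknown, hence the range from 0 to 80%. If change scores are modelled, read average change over all conditions in place of average level.

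The plan should be corrected before analysis. The consequence is confined to this exploratory work and does not touch the main cannabis-placebo comparison.

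**What to change.** In Other Effects, replace the covariate clause with:

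> *by adding to the model above, one factor at a time, the factor's main effect and its factor-by-condition, factor-by-time and factor-by-condition-by-time interactions, together with a participant-by-session random effect. We will report the difference by factor in each active-placebo contrast, at the same time points as the main contrasts, with 95% confidence intervals using small-sample degrees of freedom, labelled exploratory.*

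The Cannabis Effects paragraph does not list its contrast times, so name them there for this text to have a reference. Baseline HDRS-17 could be examined in addition to a depression diagnosis; this is optional.

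The cost is two sentences and no new data. The downside is wide intervals: state in the plan that a null result is not evidence of no influence, and that the number of intervals rules out reading isolated ones as findings.
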